To ensure optimal use of CSII and/or CGM, it is recommended that people with type 1 diabetes receive structured and recurring education (6, 7, 9). Yet, there is currently no consensus on which educational practice is best for a given patient (9, 10), and the literature indicates a paucity of high quality comparative studies regarding the effectiveness of technology-specific education (11, 12). Studies involving technology-specific education have shown that people with type 1 diabetes treated with CSII often do not use advanced pump functions or benefit substantially (13-15). These observations are concerning, particularly when combined with findings that using advanced functions can lead to improved HbA1c (16-19). It is frequently found that device-specific satisfaction is a good predictor of device utilization (20-23); however, preferences for device properties have seldomly been investigated or linked to outcomes and treatment goals of the individual (24). Whereas research mostly has focused on device-specific preferences and satisfaction (20-24), only little research has been conducted into individuals' needs and preferences for technology-specific education (12). However, meeting the needs and integrating the preferences of the individual in new interventions is considered integral to ensuring patient-centered and effective care (25-27). Accordingly, taking the target group's needs and preferences into account is essential to developing effective educational strategies (11, 25).

There are other barriers to treatment success than acquiring and maintaining the necessary skills to successfully manage CSII. For example, factors such as age and baseline HbA1c at treatment initiation have been identified as important predictors of treatment success in CSII-users (28-33).

Only a modest amount of literature has examined how psychosocial factors predict success (34, 35), with one study finding that psychological determinants, especially self-efficacy and locus of control, account for 50% of observed variation in HbA1c in people with type 1 diabetes using CSII (34). Likewise, an important known psychosocial predictor of poor diabetes outcomes is diabetes distress. One study found that a high level of diabetes distress was associated with higher HbA1c and less time in range compared to moderate or low levels of diabetes distress in people with type 1 diabetes using CSII; however, the high diabetes distress group did not perform less pump-specific

self-management activities (e.g., use of bolus wizard) suggesting that other mechanisms than technology-specific behavior may drive differences in outcomes (36). Thus, alongside demographic, socioeconomic and health status factors, psychological and psychosocial predictors may play a significant yet underexplored part in the successful use of diabetes technology.

2. Aim

The present study is part of an overarching study being conducted in Denmark at Steno Diabetes Center Copenhagen (SDCC) and Nordsjællands Hospital Hillerød (NOH), Steno Tech, that aims to develop and ultimately, in a randomized controlled trial (RCT), test approaches that can assist people with type 1 diabetes in obtaining optimal outcomes using CSII. Through a large-scale, questionnaire-based online survey enriched with data from national registers, this sub-study contributes to this overarching aim by exploring the importance of individual differences across a wide range of factors, including demographic, socioeconomic, health status, psychosocial and preference structures, for optimal use of CSII in people with type 1 diabetes.

3. Methods

3.1 Study groups/cohorts

The study population consists of two groups/cohorts:

1. Steno Tech Survey Respondents: A cohort of individuals with type 1 diabetes treated with CSII at either SDCC or NOH participating in the Steno Tech Survey.
2. General Type 1 Diabetes Population: A cohort consisting of the entire population of people with type 1 diabetes in Denmark not included in the Steno Tech Survey cohort (ca. 25.000 individuals).

3.2 Participant eligibility and selection

All adults (18+ years) with type 1 diabetes using CSII attending SDCC or NOH was invited to participate in the survey (N = 1,592); however, people who were not fluent in Danish were excluded as the survey was only available in Danish. The general type 1 diabetes group will be identified via the National Patient Registry (NPR) once data are ready for analysis (see section 3.6).

3.3 Survey recruitment procedure

Beginning in quarter 3 of 2019, eligible survey participants were approached by their primary HCP in conjunction with a consultation at SDCC or NOH and invited to participate in the survey. If they agreed to participate, they received, upon survey-opening, an invitation in e-Boks¹ with a link to the survey and a standardized, mandatory document containing information on how their data would be stored and used. Before answering the survey, participants were prompted to provide written consent.

[figure not shown]
¹ e-Boks is an electronic mailbox designed to provide a digital and secure communication path between Danish citizens, companies and public authorities. As of quarter 2 of 2019, 91.5% of all Danish citizens have an e-Boks.

3.4 Data collection procedure

The survey was designed and administered in REDCap, an online browser-based data and survey management tool. The REDCap server is encrypted, logged and administered by the Capital Region of Denmark. Thus, the tool is cleared for storing and handling person-sensitive information according to Danish law.

The survey data are to be merged with outcome and other input data from electronic medical records (EMRs) and national Danish registers and stored and analyzed on a secure server at Statistics Denmark (figure 1).

Figure 1: Overview of data sources

3.5 Survey content

The survey consisted of multiple elements as per the study aim (table 1 presents an overview, appendix 1 presents the survey in full). Importantly, this sub-study is preceded by a qualitative part of the Steno Tech Explore study that explored: 1) possibilities and barriers to effective daily insulin pump management, 2) specific circumstances and contexts in relation to the possibilities and barriers such as availability and appropriateness of structured education and other support, and 3) needs and preferences in overcoming barriers and optimizing possibilities for implementing and managing technology in daily life. The content of the survey is partly inspired by concepts and themes identified in that study and partly by systematic literature reviews (11, 12, 37, 38) and professional experience.

Table 1: Overview of survey content

Survey parts	Single survey items	Survey questionnaire scales	Survey page nrs.*
1) Insulin pump and sensor-specific characteristics and behavior	
 ♥ Type(s) of device(s) ♥ Reason(s) for device start ♥ Device functions used ♥ Data upload practices 	
Insulin Device Satisfaction Survey (IDSS)(22): consists of 13 items has three subscales: 1) perceived effectiveness, 2) burden, and 3) inconvenience.
 
Glucose Monitoring System Satisfaction Survey (GMSS)(39): consists of 15 items and has four subscales: 1) openness, 2) emotional burden, 3) behavioral burden, 4) trust.
 
New insulin pump attitude scale compiled of questions from validated scales(40, 41): included 8 items specifically about wearing an insulin pump (e.g., the degree to which it makes one feel less attractive) and everyday challenges (e.g., the degree to which it is a problem during sex).
	2-5, 10-12
2) Experience with insulin pump education	
 ♥ Received education (group/individual) ♥ Desired education (group/individual) ♥ Insulin pump-knowledge and support needs 		6-8
3) Carbohydrate counting exercise	
 ♥ Chocolate (6 images) ♥ Pasta (6 images) ♥ Grapes (6 images) ♥ Bread rolls (5 images) 	Respondents were asked to indicate if they ate the presented food items 1) never, 2) occasionally or 3) often. If occasionally or often, they were shown an image and asked to pick the serving size they would usually eat and to eyeball the amount of carbohydrates in that serving size.	9
4) Health-management behavior	
 ♥ Physical activity ♥ Diet ♥ Alcohol intake ♥ Smoking status 	Items about physical activity, diet, alcohol intake, and smoking status were based on recommended guidelines from the Danish Health Authority.	13

5) General and diabetes-specific psychosocial health		
Well-Being Index (WHO5)(42): consists of 5 items.
 
Hypoglycemia Fear Survey short-form (HFS-SF)(43): consists of 11 items and has a worry and a behavior subscale.
 
Type 1 Diabetes Distress Scale (T1-DDS)(44): consists of 28 items and has seven subscales: 1) powerlessness, 2) management distress, 3) hypoglycaemia distress, 4) negative social perceptions, 5) eating distress, 6) physician distress, and 7) friend/family distress.
 
DAWN Support for Diabetes Self-Management Profile (DSDSP) (extended)(45): this version of the DSDSP consists of 6 items.
 
The COVID-19 Impact on Quality of Life Profile(46): The COVID-19 Impact on Quality of Life Profile is a newly-designed scale, inspired by the ‘DAWN Impact of Diabetes Profile (DIDP)’ scale and consists of 9 items.
	14-16, 19-20
6) Personality factors and goal-setting	
 ♥ Self-efficacy ♥ Time preferences ♥ Risk aversion ♥ Treatment goals 	General Self-Efficacy Scale (GSE)(47): consists of 10 items.	17-18, 21-27
7) Self-rated health status and satisfaction with life	
 ♥ Health status VAS ♥ Life satisfaction VAS 	Both VAS scales ranged from 0-10, with 10 representing the best thinkable health status/satisfaction and 0 the worst.	19

Abbreviations: N/A = not applicable; VAS = visual analog scale. *Page numbers refer to actual order in the survey and correspond to appendix XX including all survey items.

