6.1 Appendix 1: The Steno Tech Survey

In the following questionnaire (see next page), the IDSS and GMSS were translated from English to Danish using the internationally recognized forward-backward translation procedure (48). Two experienced native Danish diabetes researchers fluent in English independently forward translated each scale (i.e., from English to Danish). The forward translations were then compared by a third researcher and analyzed for discrepancies, which were then discussed among all three researchers until consensus was reached. This was followed by a similar procedure, only backwards, by two other researchers, one of whom is a native English speaker fluent in Danish.

Face validity of the translated questionnaires was ensured through one-to-one interviews in the survey testing phase where, for example, the item on cost was removed from the IDSS due to irrelevance in the Danish publicly funded health care setting.

Steno Tech Explore survey

Page 1 of 28

Introductory page including information described in section 3.3.

Page 2 of 28

Scale/item [branching logic]	Question	Response categories

The first part of the questionnaire is about your insulin pump usage. There are also questions about your use of sensor, if applicable.
 
When you are done answering all the questions on a page, press “next page” at the bottom of the page in order to continue.
 
It takes about 30-40 minutes to complete the entire questionnaire. You can take a break along the way and continue the questionnaire later by simply shutting down the page and using the link in e-Boks again – disregard the “save and return later” button.
		
pumptype	
What insulin pump are you currently using? You will be shown a picture of the insulin pump below when you click on the name of the insulin pump.
	
 1. MiniMed 640G 2. MiniMed 670G 3. MiniMed Paradigm/VEO 4. Accu-Chek Combo 5. Accu-Chek Insight 6. Omnipod 7. Medtrum 8. Tandem t:slim X2 9. YpsoPump 10. Animas Vibe 11. Other 12. I use a hybrid closed-loop system that I built myself with an open-source software such as OPENAPS, AndroidAPS or Loop.
pumptype_other [if pumptype = 11]	What other insulin pump are you currently using?	Open-ended response
diabetesdebut	In which year were you diagnosed with type 1 diabetes? If you do not remember the exact year, please provide an approximate estimate.	Open-ended response

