hypow4	... low blood glucose interfering with important things I was doing	1. Never 2. Rarely 3. Sometimes 4. Often 5. Almost always
hypow5	... becoming hypoglycemic during sleep	1. Never 2. Rarely 3. Sometimes 4. Often 5. Almost always
hypow6	... getting emotionally upset and difficult to deal with	1. Never 2. Rarely 3. Sometimes 4. Often 5. Almost always

Scale/item [branching logic]	Question	Response categories

Below is a list of statements about various forms of concern that many people with type 1 diabetes experience.
 
We ask you to assess the extent to which each of the following statements has been a problem for you within the past month.
		
dds1	Feeling that I am not as skilled at managing diabetes as I should be	1. Not a problem 2. A slight problem 3. A moderate problem 4. A somewhat serious problem 5. A serious problem 6. A very serious problem
dds2	Feeling that I don't eat as carefully as I probably should	1. Not a problem 2. A slight problem 3. A moderate problem 4. A somewhat serious problem 5. A serious problem 6. A very serious problem
dds3	Feeling that I don't notice the warning signs of hypoglycemia as well as I used to	1. Not a problem 2. A slight problem 3. A moderate problem 4. A somewhat serious problem 5. A serious problem 6. A very serious problem
dds4	Feeling that people treat me differently when they find out I have diabetes	1. Not a problem 2. A slight problem 3. A moderate problem 4. A somewhat serious problem 5. A serious problem 6. A very serious problem
dds5	Feeling discouraged when I see high blood glucose numbers that I can't explain	1. Not a problem 2. A slight problem 3. A moderate problem 4. A somewhat serious problem 5. A serious problem 6. A very serious problem
dds6	Feeling that my family and friends make a bigger deal out of diabetes than they should	1. Not a problem 2. A slight problem

		
 3. A moderate problem 4. A somewhat serious problem 5. A serious problem 6. A very serious problem
dds7	Feeling that I can't tell my diabetes doctor what is really on my mind	
 1. Not a problem 2. A slight problem 3. A moderate problem 4. A somewhat serious problem 5. A serious problem 6. A very serious problem
dds8	Feeling that I am not taking as much insulin as I should	
 1. Not a problem 2. A slight problem 3. A moderate problem 4. A somewhat serious problem 5. A serious problem 6. A very serious problem

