dds18	Feeling that my diabetes doctor doesn't really understand what it's like to have diabetes	
1. Not a problem
 
2. A slight problem
 
3. A moderate problem
 
4. A somewhat serious problem

		5. A serious problem 6. A very serious problem
dds19	Feeling concerned that diabetes may make me less attractive to employers	1. Not a problem 2. A slight problem 3. A moderate problem 4. A somewhat serious problem 5. A serious problem 6. A very serious problem
dds20	Feeling that my friends or family act like “diabetes police” (bother me too much)	1. Not a problem 2. A slight problem 3. A moderate problem 4. A somewhat serious problem 5. A serious problem 6. A very serious problem
dds21	Feeling that I’ve got to be perfect with my diabetes management	1. Not a problem 2. A slight problem 3. A moderate problem 4. A somewhat serious problem 5. A serious problem 6. A very serious problem
dds22	Feeling frightened that I could have a serious hypoglycemic event while driving	1. Not a problem 2. A slight problem 3. A moderate problem 4. A somewhat serious problem 5. A serious problem 6. A very serious problem
dds23	Feeling that my eating is out of control	1. Not a problem 2. A slight problem 3. A moderate problem 4. A somewhat serious problem 5. A serious problem 6. A very serious problem
dds24	Feeling that people will think less of me if they knew I had diabetes	1. Not a problem 2. A slight problem 3. A moderate problem 4. A somewhat serious problem 5. A serious problem

		6. A very serious problem
dds25	Feeling that no matter how hard I try with my diabetes, it will never be good enough	1. Not a problem 2. A slight problem 3. A moderate problem 4. A somewhat serious problem 5. A serious problem 6. A very serious problem
dds26	Feeling that my diabetes doctor doesn't know enough about diabetes and diabetes care	1. Not a problem 2. A slight problem 3. A moderate problem 4. A somewhat serious problem 5. A serious problem 6. A very serious problem
dds27	Feeling that I can't ever be safe from the possibility of a serious hypoglycemic event	1. Not a problem 2. A slight problem 3. A moderate problem 4. A somewhat serious problem 5. A serious problem 6. A very serious problem
dds28	Feeling that I don't give my diabetes as much attention as I probably should	1. Not a problem 2. A slight problem 3. A moderate problem 4. A somewhat serious problem 5. A serious problem 6. A very serious problem

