dds29	Feeling that I can't do my job because of my diabetes	1. Not a problem 2. A slight problem 3. A moderate problem 4. A somewhat serious problem 5. A serious problem 6. A very serious problem

Scale/item [branching logic]	Question	Response categories
How supportive have the following people been in helping you to manage your diabetes in the past month?		
sos1	Your family	1. Not supportive 2. Somewhat supportive 3. Very supportive 4. Do not have these (not relevant with support from here)
sos2	Friends or other people close to you	1. Not supportive 2. Somewhat supportive 3. Very supportive 4. Do not have these (not relevant with support from here)
sos3	People at your place of work or study	1. Not supportive 2. Somewhat supportive 3. Very supportive 4. Do not have these (not relevant with support from here)
sos4	Your diabetes healthcare provider	1. Not supportive 2. Somewhat supportive 3. Very supportive 4. Do not have these (not relevant with support from here)
sos5	Other people with type 1 diabetes	1. Not supportive 2. Somewhat supportive 3. Very supportive 4. Do not have these (not relevant with support from here)
sos6	People on social media (e.g. in Facebook groups for people with type 1 diabetes)	1. Not supportive 2. Somewhat supportive 3. Very supportive 4. Do not have these (not relevant with support from here)

Scale/item [branching logic]	Question	Response categories

We want to know how you perceive your own abilities to do and achieve the things you want to in your life with diabetes.
 
Please state to what degree the following statements fit you.
		
selfeffi1	I can always manage to solve difficult problems if I try hard enough	1. Not at all true 2. Hardly true 3. Moderately true 4. Exactly true
selfeffi2	If someone opposes me, I can find the means and ways to get what I want	1. Not at all true 2. Hardly true 3. Moderately true 4. Exactly true
selfeffi3	It is easy for me to stick to my aims and accomplish my goals	1. Not at all true 2. Hardly true 3. Moderately true 4. Exactly true
selfeffi4	I am confident that I could deal efficiently with unexpected events	1. Not at all true 2. Hardly true 3. Moderately true 4. Exactly true
selfeffi5	Thanks to my resourcefulness, I know how to handle unforeseen situations	1. Not at all true 2. Hardly true 3. Moderately true 4. Exactly true
selfeffi6	I can solve most problems if I invest the necessary effort	1. Not at all true 2. Hardly true 3. Moderately true 4. Exactly true

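### Does it matter that the T1-DDS has 28 items in Table 1 but 29 in Appendix 1?

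*Combined protocol and SAP*

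**What the plan says.** Section 3.5, Table 1, part 5 (general and diabetes-specific psychosocial health) describes the distress measure as "Type 1 Diabetes Distress Scale (T1-DDS)(44): consists of 28 items and has seven subscales", and then names the seven: powerlessness, management, hypoglycaemia, negative social perceptions, eating, physician, and friend/family. The scale is tied to a numbered reference. The same section says that "appendix 1 presents the survey in full".

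In Appendix 1 (section 6.1) the distress block opens with dds1, "Feeling that I am not as skilled at managing diabetes as I should be". It runs without a gap to dds28, "Feeling that I don't give my diabetes as much attention as I probably should", and is followed by dds29, on feeling unable to "do my job because of my diabetes". All 29 share one stem and the same six response categories, from not a problem to a very serious problem.

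Two other instruments carry a note of adaptation. Appendix 1 records that "the item on cost was removed from the IDSS", and Table 1 labels the support profile as extended and adds that "this version of the DSDSP consists of 6 items". No such note appears for the T1-DDS. Section 3.7 lists psychosocial factors among the regressors of its general model. It names no distress score, subscale analysis or scoring rule.

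**The concern.** Two current parts of one plan disagree on how many items make up a scale, and neither says which items are scored. The scale is not marginal: the background states that "an important known psychosocial predictor of poor diabetes outcomes is diabetes distress", and psychosocial factors are central to the aim in section 2. With 29 variables in the dataset and 28 in the description, two analysts could in principle build different distress scores and each point to the document. Where the authors altered other instruments they said so at least twice, so silence here looks like an undeclared addition. If the odd item were folded into a short subscale, that subscale would no longer be the one in the cited instrument, and comparison with other work using the scale would suffer.

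**Working it through.** **Step 1: is the mismatch real, or is Table 1 loose throughout?** I counted the labelled items in Appendix 1 against Table 1 for every multi-item scale.

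| Scale | Table 1 | Appendix 1 |
|---|---|---|
| IDSS | 13 | 13 (idds1-9, ids10-13) |
| GMSS | 15 | 15 (gmss1-15) |
| Pump attitude | 8 | 8 (bodyimage1-8) |
| WHO5 | 5 | 5 (who51-who55) |
| HFS-SF | 11 | 5 + 6 = 11 (hypob1-5, hypow1-6) |
| DSDSP | 6 | 6 (sos1-6) |
| COVID-19 profile | 9 | 9 (covid1-9) |
| GSE | 10 | 10 (selfeffi1-10) |
| **T1-DDS** | **28** | **29** (dds1-29) |

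Eight of nine agree. The T1-DDS is the one exception, by one item.

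**Step 2: which item is the odd one?** The documents give no item key. By wording, 28 items can be placed in the seven named subscales:

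- powerlessness: 5, 9, 13, 21, 25 (5 items)
- management: 1, 8, 12, 28 (4)
- hypoglycaemia: 3, 15, 22, 27 (4)
- social perceptions: 4, 10, 19, 24 (4)
- eating: 2, 16, 23 (3)
- physician: 7, 14, 18, 26 (4)
- friend/family: 6, 11, 17, 20 (4)

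The sum is 5 + 4 + 4 + 4 + 3 + 4 + 4 = 28, and dds29 is left over. It is also last in the block. That makes it the likeliest extra item, but this is a reading of the wording. dds19, on being less attractive to employers, is also about work.

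**Step 3: effect on the total if all 29 are averaged.** With m the mean of the other 28 items and x the extra item,

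shift = (28m + x)/29 - m = (x - m)/29.

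Per point of difference this is 1/29 = 0.034. On items coded 1 to 6 the largest difference is 5, so the largest shift is 5/29 = 0.17. It needs every other item at 1 and the extra item at 6: (28 + 6)/29 - 1 = 0.17, or the reverse. A sum score would run from 29 to 174 instead of 28 to 168. Both score forms are assumptions, since the plan states neither.

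**Step 4: effect on a subscale, if someone placed the item there.** For a subscale of k items, shift = (x - m)/(k + 1). The maxima are 5/4 = 1.25 for k = 3, 5/5 = 1.0 for k = 4 and 5/6 = 0.83 for k = 5. These figures are hypothetical. No part of the plan assigns dds29 to a subscale, and by step 2 it fits none clearly, so an analyst would have no reason to put it in one.

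**Step 5: what happens under each explanation?**

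- If an item was added to the survey, the cited instrument's key does not include it, and scoring by that key leaves it out.
- If Table 1 is miscounted, the key covers all 29 and scoring by it uses all 29; Table 1 then holds a typing error.

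Either way the score is the instrument's own.

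**The case for a change.** The strongest case for acting is that the discrepancy is certain, cheap to remove and sits in a key psychosocial measure. The table in the working shows that Table 1 counts carefully elsewhere, so this is not general looseness. Without a scoring rule, the item count and the subscale names are all the plan itself gives an analyst. dds29 also has a weakness of its own: it asks about one's job with no option for people without one, whereas the support and COVID-19 items do offer a not-relevant or not-applicable answer. According to section 4, data were still being prepared for merging, so a correction would cost only a line or two.

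The count stands in full, and so does the remark about the missing response option. Two parts do not carry the weight put on them. First, that an item was added and went undeclared is an inference: the text shows 28 against 29, and two declared adaptations do not prove that every adaptation was declared. Second, the figures that look serious, up to 1.25 points, require an assignment that the plan does not make and the item's content does not invite. A smaller typical shift could be quoted by assuming a spread for the difference between dds29 and the scale mean, but the documents give no such spread, and nothing carries it through to an HbA1c coefficient.

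**Conclusion.** This is a clerical inconsistency of one item, and it does not call for a change to the plan. Analysts have a cited instrument with named subscales and would score by its key; that settles which items count without further text. The worst case for the total, if all 29 were averaged, is 0.17 on a 1-6 scale for a single respondent with the most extreme answers, and 0.034 per point of difference otherwise. No named endpoint, cut-off, sample size, power or error rate uses the number 28 or 29. Survey collection ended on October 15, 2020, so the items asked cannot change, and every response stays available for separate description.

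The conclusion rests on two assumptions: that the scale is scored by the published key, as its citation implies, and that nobody places the unmatched item in a subscale. The documents cannot show whether Table 1 or Appendix 1 holds the slip. Naming the scored items when results are reported is ordinary practice and would remove any doubt that remains.
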